1.0 Objectives

1.1 Study Objectives

The objective of this study is to determine if fluorescence lymphangiography can be used alone to localize sentinel nodes in patients with melanoma or breast cancer. The hypothesis is that sentinel nodes can be identified using only indocyanine green (ICG) and fluorescence lymphangiography, without the need for technetium99 and a gamma probe.

1.2 Primary Study Endpoints

The primary endpoint is the number of sentinel nodes correctly identified with ICG and fluorescence imaging alone.

1.3 Secondary Study Endpoints

Secondary endpoints include adverse events related to ICG and operative time for sentinel node biopsy.

2.0 Background

1.1 Scientific Background and Gaps

Sentinel node biopsy is a routine procedure in patients with both melanoma and breast cancer. The status of the sentinel node provides prognostic information and guides further treatment options in these patients. Sentinel node biopsy (SLN) was first developed using only a blue dye. Technetium99, a radioactive protein, was added later and provides the ability to image the patient and identify relevant lymph node basins. This feature is particularly important for trunk melanomas that can drain to multiple nodal basins. For the last 15 years or so, the standard method of SLN localization includes both tech99 and blue dye. While the rates of localization overall are excellent, these methods each have drawbacks.

Technetium 99 (tech99) is a radioactive protein that is injected dermally around the melanoma or the areola of the breast, usually one day prior to surgery. Lymphoscintigraphy is done 1-2 hours after injection and identifies the nodal basin that contains the sentinel node. Tech99 has an excellent track record of identifying sentinel nodes, but it does involve an extra trip to the hospital (patients are injected the day prior to surgery), the injection is often the most painful part of the entire treatment experience, and the signal can be vague and difficult to localize in the operating room. Furthermore, there are international concerns about the reliability of the supply of radio-labelled colloid. The reactors that currently provide tech99 and other radioactive substances are aging, and shortages of material have been threatened in the past.

Blue dye is injected dermally on the day of surgery, after the patient is anesthetized. This is a visual adjunct to the radioactive signal from the tech99. These two methods together have a success rate of approximately 96% in identifying the sentinel node. Blue dye alone localizes about 50% of sentinel nodes, and it can be problematic for the surgeon in that it stains tissues and is toxic to skin grafts.

Infrared lymphangiography using ICG and real time imaging has recently been used as an alternative method of sentinel node identification. The PI has recently completed an equivalency trial of tech99, Methylene blue (MB) and ICG. All subjects in this trial received all 3 dyes, and each was used simultaneously. In this study I found that tech99 and ICG are equivalent in their ability to localize sentinel nodes. MB was inferior to both, and I rarely use MB in my clinical practice now. With the experience and results from the first trial, the next question is whether we can use ICG and fluorescence imaging alone, without tech99 and the gamma probe. The SPY Elite and SPY PHI machines are FDA approved for perfusion imaging and are the devices used to identify the sentinel lymph nodes after injection of ICG.

2.1 Previous Data

Multiple centers have published their experience with fluorescence imaging to identify sentinel nodes, in both melanoma and breast cancer.¹⁻⁴ Ballardini et al⁵ found that ICG and tech99 are equivalent in identifying sentinel nodes in patients with breast cancer, and they suggest that ICG can be used alone. In our recently completed SPY trial, 89 subjects were enrolled and received tech99, MB and ICG. The tech99 identified a mean of 1.89 sentinel nodes per patient, ICG a mean of 1.87 and MB a mean of 0.71 sentinel nodes. The ICG was well tolerated, with no adverse effects noted. A drawback to the ICG is that the fluorescent signal is visible through the skin only 47% of the time. If the nodal basin is predictable, such as for an extremity melanoma or a breast cancer, we can reasonably proceed with dissection in the predicted basin. Truncal melanomas however, do not have predictable drainage and therefore the lack of visibility is problematic for using ICG alone.

2.2 Study Rationale

There is a need to develop reliable alternatives to tech99, and there is room to improve the patient experience by eliminating unnecessary injections. Prior studies have established that ICG and fluorescence imaging can reliably detect sentinel nodes, but these studies have been performed using tech99 as well. The goal of this trial is to assess our ability to identify sentinel nodes using only ICG and fluorescence imaging. This would be a significant departure from current standard practice, thus we have included a safety mechanism in the study, which is that subjects will still receive the tech99 injection, but the surgeon is blinded to the result.

3.0 Inclusion and Exclusion Criteria

3.1 Inclusion Criteria

1. HMC, Vassar Brothers Medical Center, or Emory University School of Medicine patients with melanoma or breast cancer with planned standard of care sentinel node biopsy
For melanoma patients, the melanoma should be located on the upper extremity between and including the wrist and shoulder, or the lower extremity between and including the ankle and groin.
2. Age: ≥ 18 years
3. Sex: Male or female
4. Fluent in written and spoken English

3.2 Exclusion Criteria

1. Melanoma located on the trunk, head or neck
2. Patient has an allergy to indocyanine green or sodium iodide
3. Pregnant or nursing women
4. Patients who have had a prior sentinel node biopsy in the same nodal basin
5. Prisoner
6. Cognitive impairment.

3.3 Early Withdrawal of Subjects

3.3.1 Criteria for removal from study

Subjects will be removed from the study if they withdraw consent prior to surgery. The study itself occurs only in the operating room, with no long term follow-up or involvement of the subject.

3.3.2 Follow-up for withdrawn subjects

Subjects will have sentinel node localization as per routine care if they withdraw from the study.

4.0 Recruitment Methods

4.1 Identification of subjects

Subjects will be identified by the PI and collaborating surgeons in clinic at HMC, Vasser Brothers Medical Center, or Emory University School of Medicine , at the time of their initial consultation.

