4.2 Recruitment process

Subjects will be recruited during their initial consultation or any pre-operative visit. During this visit, routine care involves counseling the patient about melanoma or breast cancer and scheduling surgery, including the sentinel node biopsy. The surgeon usually doesn't see the patient again until the day of surgery. Subjects will not be recruited on the day of surgery.

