4.4 Eligibility/screening of subjects

NA

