5.1.2 Waiver or alteration of the informed consent requirement

A waiver of consent is requested to review medical record information to determine preliminary eligibility to participate in the research.

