8.2 Sample size determination

Sample size of convenience. This is a feasibility study, and is intended to determine if fluorescence lymphangiography can be used alone to localize sentinel nodes in patients with melanoma or breast cancer. The sample size of 40 subjects is our estimation of an appropriate number of subjects such that we can draw conclusions about this technique for sentinel node biopsy, and allows sufficient numbers for multiple surgeons to be involved.

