16.3 PI Time devoted to conducting the research

The PI has dedicated time to devote to research. Furthermore, a Human Research Technologist has been hired to assist in conducting this trial.

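### The surgeons whose ICG-alone success is measured also recruit the subjects, with no consecutive-offer rule and no described record of eligible patients left out

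*Combined protocol and SAP*

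**What the plan says.** Section 4.1: "Subjects will be identified by the PI and collaborating surgeons in clinic". Section 4.2: "Subjects will be recruited during their initial consultation or any pre-operative visit"; recruitment on the day of surgery is not allowed.

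The whole entry under the 4.4 heading "Eligibility/screening of subjects" is NA. Eligibility is nevertheless checked: section 5.1.2 requests a waiver to "review medical record information to determine preliminary eligibility to participate in the research", and section 6.2 repeats this purpose.

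Sections 1.2 and 8.3 make the surgeons' results with ICG alone the primary outcome, and follow each surgeon's success over time as a learning curve. Section 7.4.3 confirms that there is no randomization. Section 8.2 calls the 40 subjects a "Sample size of convenience".

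**The concern.** In a single-group study nothing offsets case mix, so the success rate describes whichever patients were enrolled. Here the person deciding whom to approach is also the operator whose performance is the result. If patients expected to be difficult are approached less often, even without intent, the ICG-alone rate no longer describes eligible patients with a planned biopsy.

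The learning curves are exposed too. A rising success rate for a surgeon could reflect skill or a change in which cases were offered. Section 8.1 sets a goal of at least 8 subjects per surgeon, so one subject is 1/8 = 12.5 percentage points of that surgeon's rate.

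The study's stated uses depend on knowing who entered. Section 8.2 wants to draw conclusions about the technique, and section 12.2 hopes to define the patients who could avoid tech99. Without a count of eligible patients left out, a reader cannot tell how far the result carries.

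**Working it through.** **Step 1: is there a rule or a record?** There is no sample-size calculation to reproduce, because 40 is stated as a convenience number. The check is whether any section fixes who is offered the study or records who is not.

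- 4.1 and 4.2 say who identifies subjects and when. Neither asks for consecutive or all-eligible offering.
- 4.4 says NA. 5.1.2 and 6.2 describe a pre-consent record review but no log of its outcome.
- 7.2.2 has the data collection form completed per operated case, so as described it does not cover patients who never enrolled.
- 18.2 sends enrollment, consent and data collection forms to the coordinating site. These also concern enrolled subjects.
- 20.1.1 has monitors review regulatory and subject records and the collected data. No screening record is named.
- 3.1 and 3.2 narrow case mix by excluding trunk, head and neck melanoma, but they do not govern which eligible patients are approached.
- The gamma-probe check in 7.2.2 exposes nodes missed by ICG in enrolled subjects. It says nothing about patients left out.

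So, on the supplied text, there is neither a rule nor a record.

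**Step 2: how large could the effect be?** The documents give no success rate by case difficulty, so every input here is an assumption. Let *a* be success in easier cases, *b* success in harder cases, *h* the harder share among eligible patients, and *r* the enrolment rate of harder relative to easier cases.

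- Rate in all eligible patients: a(1 − h) + bh
- Harder share among enrolled: s = hr / (hr + 1 − h)
- Expected enrolled rate: a(1 − s) + bs

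With a = 0.98, b = 0.80, h = 0.30, the rate in all eligible patients is 0.98 × 0.70 + 0.80 × 0.30 = 92.6%.

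| r | s | Enrolled rate | Shift (points) | Chance of at least 38/40 |
|---|---|---|---|---|
| 1 | 0.300 | 92.6% | 0 | 42% |
| 0.5 | 0.15/0.85 = 0.176 | 94.8% | +2.2 | 66% |
| 0.25 | 0.075/0.775 = 0.097 | 96.3% | +3.7 | 81% |
| 0 | 0 | 98.0% | +5.4 | 95% |

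Range over the pairs (a, b) = (0.98, 0.80), (0.98, 0.70), (0.95, 0.85) and (0.98, 0.60), with h from 0.20 to 0.40: r = 0.5 adds 0.9 to 5.7 points, and r = 0 adds 2.0 to 15.2 points.

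**Step 3: could the enrolled data reveal it?** The exact 95% interval for 38/40 is 83.1% to 99.4%, so most of these shifts would sit within sampling error. More basically, data on enrolled subjects carry no information about patients who were not enrolled.

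**The case against.** The strongest reply is that this is a declared observational pilot with descriptive analysis and no test, so no error rate is affected. It adds that eligibility already narrows the cases, and that barring recruitment on the day of surgery prevents selection on operative findings. All of that stands. It lowers the priority of the point but does not supply the missing denominator.

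Several stronger readings are tempting and are not supported.

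- *The 47% figure gives the mechanism or the size.* Section 2.1 says "the fluorescent signal is visible through the skin only 47% of the time". That is visibility through intact skin. ICG is injected in the operating room, so visibility is unknown when the study is offered. Under 7.2.2 the imaging follows an incision over the basin, so skin visibility is not required for success. In the trial that gave 47%, ICG still found a mean of 1.87 nodes per patient against 1.89 for tech99 (1.87/1.89 = 98.9%). Section 2.1 regards lack of visibility as a problem for truncal melanoma, which is excluded here.
- *The 96% in section 2.0 is a benchmark for the result.* It is the rate for tech99 plus blue dye. The protocol sets no benchmark for ICG alone.
- *Body habitus lets a surgeon pick likely successes.* No section links it to ICG success.
- *NA in 4.4 means that eligibility goes unchecked.* Sections 5.1.2 and 6.2 show otherwise. What is missing is a record of patients not offered or declining.
- *The documents show inflation.* They show only that selection is possible and untracked.

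The data collection form and the Research Data Plan were not among the supplied text. They might hold case-mix items on enrolled subjects, but a form completed per operated case would not show who was passed over.

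**Conclusion.** The point holds as a gap in design and reporting. The surgeons whose ICG-alone success is measured also recruit the subjects, and the supplied text neither requires consecutive offering nor records eligible patients who were not offered the study or declined. Selection could affect the ICG-alone rate and the by-surgeon curves, and the report could not show or exclude it. Upward is the plausible direction, not a proven one.

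The size cannot be computed from the documents. The illustrated shifts rest wholly on assumed success rates, an assumed share of harder cases, and the assumption that surgeons can partly predict difficulty in clinic. The harm is to interpretation and generalisation. The denominator cannot be reliably rebuilt after enrolment, so the change belongs before or early in recruitment. It is a cheap improvement rather than a condition for the study to proceed.

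**What to change.** - **4.1:** state that each participating surgeon will offer the study to every eligible patient in consecutive order until total enrolment of 40 closes. Naming the total avoids confusion with the estimated site split of 20 and 20 and with the per-surgeon goal of 8.
- **4.4:** replace NA with a de-identified tally of eligible patients seen, not offered (with reason), declining and enrolled, by surgeon and by tumour type (melanoma or breast). Local staff at each site should keep it. Section 16.3 says "a Human Research Technologist has been hired to assist in conducting this trial", but 18.2 places that post at Penn State Hershey, so it does not cover the other two sites.
- **8.3:** report enrolled over eligible for each surgeon.

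Leave out patient-level features of non-enrolled patients, such as body mass index, unless the waiver is amended. Section 6.2.3 limits the waiver to determining eligibility for recruitment, and section 6.3 limits collection to essential information.

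The sample size and study procedures do not change. The cost is a little clinic time at each site and a minor wording amendment.

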4.2 Recruitment process

Subjects will be recruited during their initial consultation or any pre-operative visit. During this visit, routine care involves counseling the patient about melanoma or breast cancer and scheduling surgery, including the sentinel node biopsy. The surgeon usually doesn't see the patient again until the day of surgery. Subjects will not be recruited on the day of surgery.

4.3 Recruitment materials

None

4.4 Eligibility/screening of subjects

NA

5.0 Consent Process and Documentation

5.1 Consent Process

5.1.1 Obtaining Informed Consent

5.1.1.1 Timing and Location of Consent

Consent for the study would be obtained at the end of the clinic visit.

5.1.1.2 Coercion or Undue Influence during Consent

Subjects will be counseled that enrollment in the study is completely voluntary, and will not change their treatment. They will have a sentinel node biopsy whether they participate in the study or not, and the sentinel node is the same node whether it is localized with ICG or tech99. Subjects will also be counseled that they will still receive the tech99, as a backup plan in case the ICG doesn't work. They can think about the study and consent after the visit, although enrollment should occur at least 2 days prior to surgery to allow for notification of radiology not to mark the nodal basin.

5.1.2 Waiver or alteration of the informed consent requirement

A waiver of consent is requested to review medical record information to determine preliminary eligibility to participate in the research.

5.2 Consent Documentation

5.2.1 Written Documentation of Consent

The consent process will be documented in writing with the long form of consent documentation:

- The current IRB approved consent form will be obtained.
- We will verify that we are using the most current IRB-approved version of the study specific consent form and that the consent form is in language understandable to the subject/representative.
- A copy of the consent form will be provided to the subject/representative. Whenever possible the consent form will be provided to the subject/representative in advance of the consent discussion.
- If the subject/representative cannot read we will obtain an impartial witness to be present during the entire consent discussion to attest that the information in the consent form and any other information provided was accurately explained to, and apparently understood by, the subject/representative, and that consent was freely given.

5.2.2 Waiver of Documentation of Consent (Implied consent, Verbal consent, etc.)

NA

5.3 Consent – Other Considerations

5.3.1 Non-English Speaking Subjects

Non-English speaking subjects will not be enrolled.

5.3.2 Cognitively Impaired Adults

5.3.2.1 Capability of Providing Consent

NA

5.3.2.2 Adults Unable To Consent

Cognitively impaired adults will not be enrolled in the study.

5.3.2.3 Assent of Adults Unable to Consent

NA

5.3.3 Subjects who are not yet adults (infants, children, teenagers)

5.3.3.1 Parental Permission

NA. Melanoma is rare in children, and ICG is not approved for pediatric use.

5.3.3.2 Assent of subjects who are not yet adults

NA

6.0 HIPAA Research Authorization and/or Waiver or Alteration of Authorization

6.1 Authorization and/or Waiver or Alteration of Authorization for the Uses and Disclosures of PHI

Check all that apply:

- Not applicable, no identifiable protected health information (PHI) is accessed, used or disclosed in this study. [Mark all parts of sections 6.2 and 6.3 as not applicable]
- Authorization will be obtained and documented as part of the consent process. [If this is the only box checked, mark sections 6.2 and 6.3 as not applicable]
- Partial waiver is requested for recruitment purposes only (Check this box if patients' medical records will be accessed to determine eligibility before consent/authorization has been obtained). [Complete all parts of sections 6.2 and 6.3]
- Full waiver is requested for entire research study (e.g., medical record review studies). [Complete all parts of sections 6.2 and 6.3]
- Alteration is requested to waive requirement for written documentation of authorization (verbal authorization will be obtained). [Complete all parts of sections 6.2 and 6.3]

6.2 Waiver or Alteration of Authorization for the Uses and Disclosures of PHI

6.2.1 Access, use or disclosure of PHI representing no more than a minimal risk to the privacy of the individual

6.2.1.1 Plan to protect PHI from improper use or disclosure

Information is included in the Research Data Plan Form.

6.2.1.2 Plan to destroy identifiers or a justification for retaining identifiers

Study information will be retained until the sponsor notifies the study team that the information can be destroyed and all regulatory and institutional policies are met related to data retention.

6.2.2 Explanation for why the research could not practically be conducted without access to and use of PHI

Information must be obtained from the subject's electronic medical record during recruitment to determine eligibility and, in some cases, to confirm information discussed with the subject in regards to their medical history.

6.2.3 Explanation for why the research could not practically be conducted without the waiver or alteration of authorization

The waiver is requested only for recruitment to determine subject eligibility to ensure that no medical conditions that fall into the exclusion criteria are present and would thus preclude enrollment. This waiver will minimize the enrollment of subjects' who may ultimately fail to meet the study inclusion/exclusion criteria.

6.3 Waiver or alteration of authorization statements of agreement

Protected health information obtained as part of this research will not be reused or disclosed to any other person or entity, except as required by law, for authorized oversight of the research study, or for other permitted uses and disclosures according to federal regulations.

The research team will collect only information essential to the study and in accord with the 'Minimum Necessary' standard (information reasonably necessary to accomplish the objectives of the research) per federal regulations.

Access to the information will be limited, to the greatest extent possible, within the research team. All disclosures or releases of identifiable information granted under this waiver will be accounted for and documented.

7.0 Study Design and Procedures

7.1 Study Design

Observational pilot study.

From the subject's viewpoint, the course of events in this study will be no different than usual care and sentinel node biopsy.

7.2 Study Procedures

7.2.1 Pre-op Procedure

Subjects will have a dermal injection of technetium99 (tech99) at the melanoma tumor site prior to surgery (either the day before, or morning of surgery) or a subareolar injection if breast cancer. The surgeon will not look at the lymphoscintigraphy films, and the radiologist should not mark the skin.

7.2.2 Operative Procedure

When the subject is in the operating room and appropriately sedated or anesthetized, he or she will receive a dermal injection of indocyanine green (ICG) 0.9 ml at the melanoma tumor site or subareola if breast cancer. Incision is made in the axilla or groin, and the SPY machine is positioned over the lymph node basin. Real-time lymphangiography (SPY) is used to identify sentinel nodes. Any fluorescent nodes should be resected and are considered sentinel nodes. The absolute fluorescence will be quantified for each sentinel node. Absolute fluorescence is calculated by the SPY machine.

After the sentinel lymphadenectomy is complete but prior to closing skin, the excised lymph nodes will be examined with the gamma probe (detects tech99 signal) to confirm that they are sentinel nodes. If the node does not have a signal with the gamma probe (but is fluorescent) it is still considered a sentinel node. The lymph node basin will also be examined with the gamma probe, to insure that no sentinel nodes are missed. If a gamma positive sentinel node is identified in the lymph node basin, it should be resected and imaged with SPY. If no sentinel nodes are able to be identified with fluorescent imaging, the gamma probe will be used as per usual practice. The surgeon should spend no more than 30 minutes using SPY to identify sentinel

nodes. If after 30 minutes no sentinel node is found, the gamma probe should be used. The data collection form (separately uploaded) should be completed for each case.

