8.3 Statistical methods

The analysis of these results will be descriptive. We will assess the number of nodes per patient that are correctly identified with ICG alone, and the number of patients in whom ICG was successfully used

alone. Multiple surgeons will be involved, some with more experience than others with this technique. We will assess the learning curve by studying the success rate with ICG over time for each surgeon.

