10.0 Data and Safety Monitoring Plan

10.1 Periodic evaluation of data

Collaborating surgeons will be monitored for at least 3 subjects, or until they demonstrate proficiency with ICG and the SPY device. Proficiency of each surgeon will be assessed by the PI or a representative from Stryker prior to each surgeon enrolling patients. While observing the collaborating surgeons for training purposes, the PI or a representative from Stryker will look for competence in and understanding of the use of the SPY machine. Each surgeon should demonstrate an understanding of the images that they are looking at on the SPY machine during the procedure. After 10 subjects, the PI will review the cases to insure that sentinel nodes are being identified for each subject.

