10.2 Data that are reviewed

Any adverse events that occur during surgery, whether deemed related to the ICG or not, will be reviewed. Adverse events will include reactions to ICG such as hives. Efficacy will be determined by success rates of localizing sentinel nodes with ICG alone.

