11.0 Risks

- Loss of confidentiality
- Adverse reactions to ICG are extremely rare, and none occurred in the prior trial with 87 subjects.
- Anaphylactic reactions, urticarial reactions and headache have been reported rarely in some patients.
- The risks of sentinel node biopsy are usual care as the subjects will undergo the biopsy regardless of their participation in the research. However, there is the possible risk of longer surgery, with a maximum of 30 additional minutes under anesthesia. This added time is of no consequence to the patient and carries an unmeasurable risk. Inaccurate identification of the sentinel node may occur equally in patients both on and off this study, therefore the risk in this study is no greater than usual care. The false negative rate in identifying sentinel nodes is 8%. Tech99 is used as a backup in this study in the event that the sentinel node cannot be identified with ICG.

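### The primary endpoint counts ICG-identified nodes without dividing by all sentinel nodes, so it does not show how many only the gamma probe found

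*Combined protocol and SAP*

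**What the plan says.** Section 1.2 states: "The primary endpoint is the number of sentinel nodes correctly identified with ICG and fluorescence imaging alone". Section 8.3 makes the analysis descriptive and expresses that count by patient: "We will assess the number of nodes per patient that are correctly identified with ICG alone". It adds a patient-level count, "the number of patients in whom ICG was successfully used" on its own, and a per-surgeon analysis: "We will assess the learning curve by studying the success rate with ICG over time for each surgeon". Section 10.2 says: "Efficacy will be determined by success rates of localizing sentinel nodes with ICG alone". None of these gives a node-level denominator or defines success.

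Section 7.2.2 sets the order of events. The surgeon works with fluorescence first, and every fluorescent node is resected and called sentinel. The excised nodes are then checked with the gamma probe, but a negative reading changes nothing: "If the node does not have a signal with the gamma probe (but is fluorescent) it is still considered a sentinel node". The probe next goes over the basin to look for missed nodes. A gamma-positive node found there is resected and imaged with SPY. If fluorescence finds no node at all, the gamma probe takes over.

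Two further passages bear on what success might mean. Section 10.1: "After 10 subjects, the PI will review the cases to insure that sentinel nodes are being identified for each subject". Section 11.0: "Tech99 is used as a backup in this study in the event that the sentinel node cannot be identified with ICG".

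**The concern.** The hypothesis in section 1.1 is that sentinel nodes can be found without technetium and a gamma probe. The direct evidence on it is the set of nodes that ICG left behind and the gamma sweep then found. The procedure yields those nodes, but no stated node-level measure uses them.

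Three gaps combine.

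- **No denominator.** The count is divided by patients, not by sentinel nodes. Because every fluorescent node is sentinel by definition, no fluorescent node can be scored as incorrect, and fluorescent-only nodes can offset gamma-only misses in the total.
- **No definition of patient-level success.** The idea of ICG used alone, read with the sweep for missed nodes, suggests that nothing was missed. The fallback in 7.2.2, the backup statement in 11.0 and the case review in 10.1 suggest that finding one node is enough. The same undefined term feeds 10.2 and the learning curve.
- **No rule for a node first found by the gamma probe that then fluoresces.** If it counts as ICG-identified, a node found by gamma probe enters the primary figure as an ICG success.

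The trial has no test or threshold, so no error rate is at stake. What is at stake is whether the headline figure answers the question, given that 8.2 says 40 subjects should be enough to support conclusions about the technique. Choosing the success definition after the data are seen would also leave room for the favourable one.

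**Working it through.** There is no formula-based figure to reproduce: 40 is a sample of convenience (8.2), and the site split of 20 + 20 = 40 (8.1) adds up. The check asks how far the miss rate can move while the primary count stays still.

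**Inputs.** 40 subjects (8.1). Earlier-trial means per patient of 1.87 nodes by ICG and 1.89 by technetium (2.1). The overlap between methods is not given and is assumed.

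**Totals.** 1.87 × 40 = 74.8, about 75 fluorescent nodes. 1.89 × 40 = 75.6, about 76 gamma-positive nodes. Both are held fixed, and no gamma-found node is assumed to fluoresce later.

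**Node level.** Let m be the number of gamma-positive nodes that ICG missed. Nodes positive on both methods = 76 − m. Fluorescent-only nodes u = 75 − (76 − m) = m − 1. All sentinel nodes by either method = 75 + m.

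| m | u | Primary count | Share of either-method nodes, 75/(75 + m) | Share of gamma-positive nodes, (76 − m)/76 |
|---|---|---|---|---|
| 1 | 0 | 75 (1.88 per patient) | 75/76 = 98.7% | 75/76 = 98.7% |
| 8 | 7 | 75 (1.88 per patient) | 75/83 = 90.4% | 68/76 = 89.5% |
| 15 | 14 | 75 (1.88 per patient) | 75/90 = 83.3% | 61/76 = 80.3% |

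The earlier trial's means have the same limitation. With 89 subjects (2.1), 89 × 1.89 ≈ 168 and 89 × 1.87 ≈ 166. Those totals alone are compatible with ICG missing anything from 2 to all 168 technetium nodes. Using the 87 subjects given in 10.5 and 11.0, the range is 1 to 164. Near-equal means do not show node-by-node agreement.

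**Patient level.** Assume 1 + Poisson(0.89) gamma-positive nodes per patient (mean 1.89), fluorescent-only nodes Poisson(u/40) and independent of misses, p = (76 − m)/76 and q = 1 − p.

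- Independent nodes: P(none missed) = p·exp(−0.89q), and P(at least one found) = 1 − q·exp(−0.89p)·exp(−u/40).
- Full within-patient correlation: P(none missed) = p, and P(at least one found) = 1 − q·exp(−u/40).
- Example, m = 8, independent: none missed = 0.8947 × exp(−0.89 × 0.1053) = 81.5%; at least one found = 1 − 0.1053 × exp(−0.89 × 0.8947) × exp(−0.175) = 96.0%.

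Every modelled patient has a gamma-positive node, so none missed also implies at least one found.

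| m | Independent: at least one found v none missed | Gap (points) | Full correlation: at least one found v none missed | Gap (points) |
|---|---|---|---|---|
| 1 | 99.5% v 97.5% | 1.9 | 98.7% v 98.7% | 0.0 |
| 8 | 96.0% v 81.5% | 14.5 | 91.2% v 89.5% | 1.7 |
| 15 | 93.2% v 67.3% | 25.9 | 86.1% v 80.3% | 5.8 |

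Gaps come from unrounded values. Intermediate correlations fall between the two extremes.

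**Precision of a node-level share at m = 8.** The Wilson 95% interval for 75/83 is 82.1% to 95.0% with no clustering. With full clustering, either-method nodes per patient are 1 + Poisson(0.89 + 7/40), with mean 2.065. The design effect is E[N²]/E[N] = (1.065 + 2.065²)/2.065 = 2.58, the effective n is 83/2.58 = 32.2, and the interval is 75.5% to 96.6%. For 68/76 gamma-positive nodes (design effect 2.36) the intervals are 80.6% to 94.6% and 74.4% to 96.1%.

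**The case against.** This is a descriptive pilot of convenience size. The gamma sweep produces the missing information, and the separately uploaded data collection form, which was not available for review, may record it node by node. Reading the patient-level count together with the sweep points towards success meaning that nothing was missed, and 10.2 speaks of rates, which implies some ratio. The passages that suggest at least one node is enough are an operative fallback, a risk statement and an early case review; none defines an endpoint. Adding a line on gamma-only nodes might be enough without replacing the endpoint.

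The illustration also builds in its result. Fixing both totals forces each extra miss to be offset by a fluorescent-only node. The means come from a trial in which all agents were used simultaneously (2.0), whereas here ICG comes first. The patient-level gap starts at zero, and its upper end needs about 20% of gamma-positive nodes missed with independence between nodes.

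These limits on the illustration stand: it shows what the count can hide, not what is likely. The point about data capture also stands, so the concern is about the defined measure and not about lost data. But neither 1.2 nor 8.3 divides by sentinel nodes, and no passage commits to reporting gamma-only nodes. A reasonable inference about success is not a definition that several surgeons at three sites would apply alike. As for replacing the endpoint, the planned count survives as the numerator, subject to the scoring rule for gamma-found nodes.

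**Conclusion.** The concern holds and should be fixed. Followed exactly, the plan yields a primary figure that does not show the miss rate on which the hypothesis turns. In the illustration the figure stays at 75 nodes while the either-method share falls from 98.7% to 83.3% and the share of gamma-positive nodes from 98.7% to 80.3%. For patient-level success, the choice of reading moves the result by 1.7 to 14.5 points in the 8-miss case, and by 0 to 25.9 points over all three.

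The sizes depend on the assumed overlap, the fixed totals, the patient-level distributions and the absence of gamma-found nodes that later fluoresce. The missing denominator and the undefined success do not depend on those assumptions; they follow from 1.2, 7.2.2 and 8.3 as written.

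**What to change.** Change scoring and reporting only; which nodes are resected stays as it is. In 1.2, 8.3 and 10.2:

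1. **Node level.** Replace the count with a proportion under the protocol's own either-method definition: nodes removed in the ICG phase before the gamma probe was used, divided by all sentinel nodes removed by either method. Fluorescent-only nodes raise this figure, so report beside it the share of gamma-positive nodes removed in the ICG phase. Also give the counts positive on both methods, fluorescent-only and gamma-only. Attach descriptive 95% intervals that allow for nodes clustered within subjects.
2. **Patient level.** Define ICG-alone success as at least one node removed in the ICG phase and no further gamma-positive node found by the sweep. Use this for the rates in 10.2 and the learning curve in 8.3, and state how many successes had no gamma-positive node.
3. **Scoring rule.** A node first found by the gamma probe is an ICG miss even if it fluoresces afterwards. If fluorescence finds no node in a subject, all of that subject's nodes are misses.

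Confirm that the data collection form records phase of removal and gamma status for each node.

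The cost is wording in three sections and possibly one form field. The downside is a success figure that may look less favourable and will have a wide interval.
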